#### **4.5 Definition of Completed Subjects**

A subject will be considered as having completed the trial after completion of their final trial visit (ET, or Week 52/EOT). Safety Follow-up Visit data summarization and analysis will be performed separately.

Subjects who discontinue prematurely from the trial will complete the ET Visit assessments and will complete the Safety Follow-up Visit, 4 weeks after their last dose of IMP.

The need for rescue therapy does not constitute trial completion unless it meets the criteria stated in [Section 7.3.2](#). Also, the occurrence of a safety endpoint does not constitute trial completion and is not a criterion for subject withdrawal from the trial or IMP (vadadustat or darbepoetin alfa).

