### 7.3.2 Treatment Discontinuation

After treatment assignment, a subject may stop treatment permanently for a variety of reasons. Treatment discontinuations may be initiated by a subject who is not satisfied with treatment or may become medically necessary due to AEs, required treatment with a disallowed medication or therapy, or other issues, as determined by the investigator.

However, each investigator must comprehensively review the circumstances and offer the subject options for continued treatment to the degree possible. If, after discussion with the investigator about possible mitigations for AEs, etc., the subject still chooses to discontinue IMP, the subject will permanently discontinue IMP and will complete the ET Visit assessments and will complete the Safety Follow-Up Visit, 4 weeks after last dose of IMP and the subject will not be allowed to re-start the IMP.

Trial medication is to be permanently discontinued if ESA rescue (other than darbepoetin alfa in comparator arm, any ESA in vadadustat arm) is not in the setting of acute bleeding (ie, gastrointestinal bleed, surgery, excess bleeding) and one of the following:

- The first cycle of ESA rescue lasts >30 days or
- Subject requires a second cycle of ESA for rescue (that must be related to anemia) at any time.

Trial medication must be permanently discontinued if a subject meets one of the criteria in [Table 7.3.2-1](#).

Table 7.3.2-1 Trial Medication Stopping Rules	
ALT or AST > 3x ULN and total bilirubin > 2x ULN	Permanently Discontinue Treatment
ALT or AST > 3x ULN and INR > 1.5	Permanently Discontinue Treatment
ALT or AST > 8x ULN	Permanently Discontinue Treatment
ALT or AST remains > 5x ULN over 2 weeks a	Permanently Discontinue Treatment
ALT or AST > 3x ULN with symptoms including eg, fatigue, nausea, vomiting, right upper quadrant pain, fever, rash or eosinophilia	Permanently Discontinue Treatment

INR: international normalized ratio; ULN: upper limit of normal

aRe-challenge generally should be avoided with ALT or AST > 5x ULN unless there are no other good therapeutic options.

See [Section 8.8](#) for reporting requirements related to a subject being permanently discontinued based on meeting the laboratory abnormalities list above in [Table 7.3.2-1](#).

For subjects who permanently discontinue IMP, the investigator will resume standard of care treatment, including ESAs and iron therapy, as deemed appropriate.

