A suspected adverse reaction is any AE for which there is a reasonable possibility that the IMP caused the AE. For the purpose of Investigational New Drug (IND) safety reporting, "reasonable possibility" means there is evidence to suggest a causal relationship between the IMP and the AE. Suspected adverse reaction implies a lesser degree of certainty about causality.

Treatment-emergent AEs (TEAEs) are defined as AEs with an onset date on or after the start of open-label treatment. In more detail, TEAEs are all adverse events which started after start of open-label IMP treatment; or if the event was continuous from baseline and was worsening, serious, IMP related, or resulted in death, discontinuation, interruption or reduction of IMP.

The sponsor maintains and updates a listing of any adverse event of special interest (AESI), serious or non-serious, which is of scientific and medical concern specific to the sponsor's product or program, for which ongoing monitoring and rapid communication by the investigator to the sponsor could be appropriate.

A SAE includes any event that results in any of the following outcomes:

- Death.
- Life-threatening; Life threatening is defined as any event in which the subject was at risk of death at the time of the event; 'life-threatening' does not refer to an event which hypothetically might have caused death if it were more severe. For example, drug-induced hepatitis that resolved without evidence of hepatic failure would not be considered life threatening, even though drug-induced hepatitis of a more severe nature can be fatal.
- Persistent or significant incapacity/disability or substantial disruption of the ability to conduct normal life functions.
  - Disability is defined as a substantial disruption in a person's ability to conduct normal life functions.
- Requires inpatient hospitalization or prolongs hospitalization.
  - Hospitalization is defined as an overnight admission with observation of a minimum of 24 hours. A hospitalization planned before the start of the trial for a pre-existing condition that has not worsened during the AE reporting period does not constitute an SAE unless an untoward event occurs related to the procedure (eg, elective hospitalization for a total knee replacement due to a pre-existing condition of osteoarthritis of the knee that has not worsened during the course of the trial).
- Congenital anomaly/birth defect.

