#### **8.8.2.1 Guidelines for Reporting Adverse Events**

Each AE is to be classified by the investigator as SERIOUS or NONSERIOUS and all AEs (serious and non-serious) are to be reported on the AE eCRFs.

All AEs that occur in trial subjects during the AE reporting period specified in this protocol must be reported, whether or not the event is considered related to IMP (vadadustat or darbepoetin alfa). In addition, each trial subject will be questioned about AEs at each visit following the initiation of treatment as described in [Section 8.8.2](#).

The AE collection for this trial begins from time of ICF signing through the Safety Follow-up Visit.

In addition, any AE that occurs subsequent to the AE reporting period that the investigator assesses as related to the IMP should also be reported as an AE.

The following guidelines are to be used when reporting AEs for this trial:

**Medical Diagnoses** – Whenever possible, a medical diagnosis term should be used to report AEs instead of signs and symptoms due to a common etiology, as determined by qualified medical trial staff. For example, pneumonia should be the reported AE term, instead of fever and dyspnea, when the diagnosis has been established. Signs and symptoms should be reported as event terms only when the medical diagnosis remains unknown and revised to a medical diagnosis term once it has been established.

**Procedures** – Diagnostic and therapeutic non-invasive and invasive procedures, such as surgery, should not be reported as AEs. However, the medical condition for which the procedure was performed should be reported if it meets the definition of an AE. For example, an acute appendicitis that begins during the AE reporting period should be reported as the AE and the resulting appendectomy noted under “Comments”.

Pre-planned therapeutic procedures not associated with a new medical condition or worsening pre-existing condition should not be reported as AEs.

**Pre-existing Conditions** – In this trial, a pre-existing condition (ie, a disorder present before the AE reporting period started and noted on the pretreatment medical history/physical examination form) should not be reported as an AE unless the condition worsens or episodes increase in frequency during the AE reporting period.

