##### **9.4.2.1 Adverse Events**

Adverse events will be summarized using the number and percentage of subjects with AEs for all subjects in the safety population. Summaries will also be provided for subgroups including Region, Age, Gender, and Race.

All AEs will be coded using Medical Dictionary for Regulatory Activities (MedDRA). Treatment-emergent and post-treatment AEs will be summarized by SOC and preferred term for each treatment group. Adverse events will also be summarized by their maximum severity.

Summaries will also be provided for the following types of AEs:

- SAEs.
- Related AEs (including all categories for relationship to IMP other than “Unrelated”, as determined by the investigator).
- AEs leading to early discontinuation of IMP.
- Summaries on adjudicated events (see [Section 9.5](#)) will be provided by treatment group.

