HLGT	High-Level Group Term
HLT	High-Level Term
HRQOL	Health-Related Quality of Life
IDMC	Independent Data Monitoring Committee
IMP	Investigational Medicinal Product
ISS	Integrated Safety Summary
IV	Intravenous
IWR	Interactive Web Response
LLD	Lower Limits of Detection
MCS	Mental Summary Component
MedDRA	Medical Dictionary for Regulatory Activities
MH	Mental Health
MMRM	Mixed Models for Repeated Measurements
NDA	New Drug Application
NEC	Not Elsewhere Classified
NYHA	New York Heart Association
PCS	Physical Summary Component
PD	Pharmacodynamic
PEP	Primary Efficacy Period
PF	Physical Functioning
PGI-C	Patient Global Impression of Change
PGI-S	Patient Global Impression of Severity
PGx	Pharmacogenomic
PI	Package Insert

Abbreviation	Definition
PK	Pharmacokinetic
PP	Per Protocol
PT	Preferred Term
QD	Once Daily
RBC	Red Blood Cell
RE	Role-Emotional
RP	Role-Physical
SAE	Serious Adverse Event
SAP	Statistical Analysis Plan
SC	Subcutaneous
SEAC	Safety Event Adjudication Committee
SEP	Secondary Efficacy Period
SF	Social Functioning
SF-36v2	36-Item Short Form Version 2
SmPC	Summary of Product Characteristics
SMQ	Standardised MedDRA Query
SOC	System Organ Class
TEAE	Treatment-Emergent Adverse Event
TIBC	Total Iron Binding Capacity
TIW	Three Times Weekly
TSAT	Transferrin saturation
ULN	Upper Limit of Normal
US	United States
[REDACTED]	[REDACTED]
VT	Vitality
WBC	White Blood Cells
WNL	Within Normal Limits

1 Introduction

This statistical analysis plan (SAP) covers the 404-201-00012 MO₂DIFY Study.

The SAP supports the Statistical Methods Section and documents the pre-planned statistical analyses plan of the clinical study report (CSR). It elaborates upon the protocol-specified endpoint definitions and the formal statistical methods that will be used in analyzing the study. Unless otherwise specified, all analyses will be conducted. If the analyses described in the protocols differ from those in this SAP, the methods of the SAP prevail.

2 Description of the Studies

This study is a phase 3b, randomized, open-label, active-controlled trial evaluating the efficacy and safety of oral vadadustat once daily (QD) and three times weekly (TIW) for the maintenance treatment of anemia in hemodialysis subjects converting from erythropoiesis-stimulating agents (ESAs).

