10.3 Adverse Events and Serious Adverse Events

The AE eCRF has been designed to capture all events from time of signing the informed consent through the Safety Follow-up visit. Subjects must be followed for AEs until the final required protocol visit or until all drug-related toxicities and serious adverse events (SAEs) have resolved (or are considered chronic/stable), whichever is later. All AEs will be coded by Medical Dictionary for Regulatory Activities (MedDRA) system organ class (SOC) and preferred term (PT). The MedDRA version used for reporting this study will be described in a footnote on AE related outputs.

Treatment-emergent AEs (TEAEs) are defined as AEs with an onset date on or after the start of IMP treatment. In more detail, TEAEs are all adverse events which started after start of IMP treatment; or if the event was continuous from baseline and was worsening, serious, IMP related, or resulted in death, discontinuation, interruption or reduction of IMP.

All TEAE summaries will provide the number of subjects reporting at least 1 TEAE. Tables will present the number and percentage of subjects by treatment group reporting at least 1 of the following:

- TEAE, SOC, and PT
 - TEAE leading to withdrawal of study medication, SOC, and PT
 - TEAE, severity, SOC and PT
 - Drug-related TEAE, SOC, and PT
 - Drug-related TEAE leading to withdrawal of study medication, SOC, and PT
- Treatment-emergent SAE, SOC, and PT
 - Drug-related treatment-emergent SAE, SOC, and PT
 - Fatal TEAE, SOC and PT.

A summary table will show number of subjects with at least 1 of each of the following:

- AE,
- SAE,
- TEAE,
- Severe TEAE
- TEAE leading to withdrawal of study treatment,

- Drug-related TEAE leading to withdrawal of study treatment,
- Drug-related TEAE,
- Treatment-emergent SAE,
- Drug-related treatment-emergent SAE,
- Fatal TEAE,
- All death.

TEAEs reported at least 5% of subjects in any treatment groups, and non-serious TEAEs reported at least 5% of subjects in any treatment groups will be summarized by SOC and PT for each treatment group.

TEAEs will be summarized by 1) worst severity, and 2) worst causality by SOC and PT. For each subject and each PT, the worst severity recorded will be used in the by-severity summaries. Similarly, the most conservative causality assessment (most related to treatment) will be attributed and used in the by-causality summaries. If severity or causality is missing, data will be imputed to the worst category.

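### The TEAE definition has a start but no end, and the post-treatment AE summary that Protocol 9.4.2.1 asks for is neither defined nor planned in the SAP

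*SAP*

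**What the plan says.** SAP 10.3 sets the rule: "Treatment-emergent AEs (TEAEs) are defined as AEs with an onset date on or after the start of IMP treatment". The sentence after it adds events continuing from baseline that worsen or meet certain other conditions, and sets no end either. Protocol 8.8.1 matches: "Treatment-emergent AEs (TEAEs) are defined as AEs with an onset date on or after the start of open-label treatment".

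Collection does have a limit. SAP 10.3 says "The AE eCRF has been designed to capture all events from time of signing the informed consent through the Safety Follow-up visit". The limit is not absolute, because under Protocol 8.8.2.1 "any AE that occurs subsequent to the AE reporting period that the investigator assesses as related to the IMP should also be reported".

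On reporting, Protocol 9.4.2.1 says "Treatment-emergent and post-treatment AEs will be summarized by SOC and preferred term for each treatment group". Protocol 4.5 says "Safety Follow-up Visit data summarization and analysis will be performed separately", and Section 4.1 and the synopsis repeat it. SAP 10.3 and the table list in SAP Section 19 contain no adverse event output for the post-treatment or follow-up period. Where the two documents differ on analyses, SAP Section 1 states that "the methods of the SAP prevail".

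For subjects who stop IMP permanently, Protocol 7.3.2 says "the investigator will resume standard of care treatment, including ESAs and iron therapy, as deemed appropriate".

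**The concern.** Read as written, the definition makes every event with onset after the first dose treatment-emergent, including one that begins weeks after the last dose. The protocol nevertheless treats post-treatment events as something to be shown. A programmer following the SAP would produce the first set of tables and not the second.

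The same rule can mean different things in different arms. A control subject who stops IMP and returns to an ESA typically stays on the same drug class. A vadadustat subject who does so has changed drug, and an event starting on the ESA would still appear in the vadadustat column. The comparison with an ESA is the safety half of the primary objective, and Protocol 2.1 and 4.2 cite ESA cardiovascular and mortality risks as background, so attribution matters here.

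The SAP draws the line elsewhere. Rescue therapy (SAP 6.4) excludes treatment that starts after permanent discontinuation, and concomitant medication (SAP 5.3) ends at the last IMP dose. An ESA first resumed after the last vadadustat dose therefore falls outside the concomitant-medication definition, while an event that starts on it is inside the TEAE definition.

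**Working it through.** **1. The texts side by side.**
- Start of the TEAE window: first IMP dose (SAP 10.3; Protocol 8.8.1).
- End of the TEAE window: not stated in either document.
- Definition of a post-treatment AE: not stated in either document.
- Post-treatment AE summary: asked for in Protocol 9.4.2.1, absent from SAP 10.3 and SAP Section 19.

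**2. The plan's own figure.** Screening of up to 8 weeks, treatment of 52 weeks and follow-up of 4 weeks give 8 + 52 + 4 = 64 weeks. This reproduces the approximate individual duration in Protocol 4.1 and supports a nominal tail of 4 weeks.

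**3. Length of the tail.** Protocol Section 8 places the Follow-up Visit 4 weeks after EOT, or 4 weeks after the last dose for early termination. The ET assessments may come up to 7 days after stopping IMP, and the synopsis times follow-up at 4 weeks after the ET visit, with a 7-day allowance. The longest usual tail is 1 + 4 + 1 = 6 weeks. A completer has no ET visit, so using 6 weeks for everyone overstates the upper end.

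**4. Share for one subject.** Off-drug share = tail / (weeks on treatment + tail). With a 4-week tail:
- Completer: 4/(52 + 4) = 7.1%
- Stop at Week 26: 4/(26 + 4) = 13.3%
- Stop at Week 8: 4/(8 + 4) = 33.3%

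**5. Share for an arm of 100.** Protocol 9.3 expects up to 30% to discontinue. The stop times below are assumptions, because the documents give none. Everyone is taken to complete the tail.
- 30 stops spread evenly over 52 weeks (mean 26): on-treatment time is 70 × 52 + 30 × 26 = 4,420 person-weeks. The share is 400/4,820 = 8.3% with a 4-week tail and 600/5,020 = 12.0% with 6 weeks.
- All 30 stop at Week 8: on-treatment time is 70 × 52 + 30 × 8 = 3,880 person-weeks. The share is 400/4,280 = 9.3% with 4 weeks and 600/4,480 = 13.4% with 6 weeks.

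The range is roughly 8% to 13%.

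**6. What cannot be computed.** The documents give no adverse event rates, and the planned tables count subjects with at least one event, not person-time. An event in the tail changes a count only if the subject has not already had that event. These shares are therefore not estimates of misattributed events.

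**The case against.** Counting all events through follow-up is a legitimate convention. Collection stops at the Safety Follow-up Visit in every arm, so the working definition is close to last dose plus about 4 weeks. Protocol 4.3 says mean Hb falls within 2 to 4 weeks of stopping, so an event in that time may still reflect the drug. A cut at the last dose alone would move such events out of the drug's column. This stands, and it is the reason to keep the existing tables.

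Most of the tail also belongs to completers: 70 × 4 = 280 of the 400 person-weeks. Not every discontinuation leads to ESA time, since the reasons in Protocol 7.3 include death, loss to follow-up and transplantation, and ESAs are resumed only as judged appropriate. Deaths (SAP 10.1) and adjudicated cardiovascular events (SAP 10.4) are summarized by arm in their own right, so those results do not rest on the TEAE tables alone. All of this limits the consequence.

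It can also be said that the two categories need not exclude each other, so a post-treatment summary could overlap with TEAEs, or that the separate Safety Follow-up analysis could be reported elsewhere. Neither document says so. On either reading the SAP still lacks a definition and a table.

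Some stronger readings are tempting but not supported:
- **That the post-treatment table is impossible.** The AE listing carries onset day and study drug administration is listed, so it can be made once a cut-off is stated.
- **That the window is unlimited in practice.** The usual bound is 4 to 6 weeks. Late related events, and the transplant recipients whom Protocol 8.8.2.1 keeps on the visit schedule, are exceptions.
- **That about half of an early stopper's time is off drug**, by adding a 30-day interruption before exit to a further 4 weeks of follow-up. This needs follow-up timed from the ET visit (Protocol 7.3, synopsis), whereas Protocol 4.5, 7.3.2 and Section 8 time it from the last dose.

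**Conclusion.** The point holds as a conflict between the documents with a practical consequence. The TEAE rule has no end, events after permanent discontinuation are tabulated under the subject's trial treatment, and a summary named in the protocol is neither defined nor planned. The protocol shares the gap, since its Section 8.8.1 definition leaves no distinct class for the post-treatment events in its Section 9.4.2.1.

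The tail is about 7% of a completer's observation time, 33% for a stop at Week 8, and roughly 8% to 13% of an arm's person-time. The arm figures rest on 30% discontinuation, assumed stop times and a tail of 4 to 6 weeks. A reader might infer that the rule pulls the arms together or hides a cardiovascular signal. That is plausible but cannot be shown: without event rates, neither the size nor the direction of an effect on counts can be derived. No primary efficacy result, alpha or power figure is affected. The change should be made, given its low cost and the safety comparison it serves.

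**What to change.** In SAP 10.3:
- Keep the current TEAE tables through follow-up.
- Add a split by onset date, applied identically in all arms: on treatment (first dose through last IMP dose) and post-treatment (onset after the last IMP dose). The cut belongs at the last dose because a window of about 4 weeks beyond it would reclassify almost nothing.
- Produce the SOC and preferred-term summary for each part, which meets Protocol 9.4.2.1, and list the new tables in SAP Section 19.
- As an addition that the protocol does not itself require, show SAEs, fatal events and AESIs for both parts.
- State in the SAP how the separate Safety Follow-up summarization in Protocol 4.1 and 4.5 will be delivered.

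A flag for events with onset while vadadustat is interrupted for an ESA is optional, since it concerns time before the last dose.

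The cost is SAP wording, one derived flag and a few tables; no new data are needed. Counts per table will be smaller, and some delayed drug effects will fall in the post-treatment table, but the retained through-follow-up table still captures them. The cut-off should be fixed before by-treatment results are seen, because in an open-label trial a later choice could look data-driven.

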### Screening Visits

The ICF will be signed at Screening Visit 1. Subjects will need to sign the ICF prior to any Screening Visit 1 procedures. The Screening period starts at the time the ICF is signed and will be up to 8 weeks in duration. Two Screening visits must be performed within 8 weeks prior to dosing (Baseline Visit/Day 1). There must be a minimum of 4 days between the 2 Screening Visits and a minimum of 4 days (based on last ESA use) between Screening Visit 2 or last retest and the Baseline Visit.

The investigator will maintain a log of subjects and indicate who of the Screened subjects were enrolled or excluded and the reason for exclusion.

After obtaining informed consent, subjects will undergo a number of screening activities.

Two Hb values, at least 4 days apart, measured by the central laboratory during Screening must be between 8.0 and 11.0 g/dL (inclusive) in the US or between 9.0 and 12.0 g/dL (inclusive) in Europe to qualify for inclusion into the trial. If the subject’s Hb does not qualify after Screening Visit 1, Screening Visit 2, or retest Hb, the subject should be considered a Screen failure. Refer to [Section 5.4.1](#) for further details regarding repeating laboratory measurements during the Screening period.

For all subjects, it is recommended that no additional ESA doses be administered after Screening Visit 2 and prior to the Baseline Visit (Day 1).

For all subjects, it is required that a minimum period as outlined below be observed between the last dose of ESA administered during Screening and Randomization Visit:

- 2 days after last dose of epoetin analogues.

- 7 days after last dose of darbepoetin alfa.
- 14 days after last dose of methoxy polyethylene glycol-epoetin beta.

After discussion with the Medical Monitor, screening may be extended for an additional 2 to 4 weeks based on the subject's Hb level or Hb trajectory or based on timing of the last ESA dose given during screening.

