### **8.8      *Adverse Events***

AE collection will begin from time of signing the ICF through the Safety Follow-up Visit. The investigator and trial personnel will review each subject's laboratory and clinical evaluation findings and query the site directly regarding AEs (see [Section 8.8.1](#)). Subjects must be followed for AEs until the final required protocol visit or until all drug-related toxicities and SAEs have resolved (or are considered chronic/stable), whichever is later.

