5.4 Handling of Missing Data

Missing data will be handled using a procedure specific to each variable and analysis as described in the sections relevant to each endpoint. If no method for missing data is discussed, descriptive analyses will be based upon observed data without imputation.

For the analysis of safety variables, only partial dates will be imputed unless otherwise specified. The algorithms for imputation of partial dates depend upon the parameter, as follows.

Adverse event onset

- If onset date is completely missing, date is set to date of first dose.
- If year is present and month and day are missing, or year and day are present, but month is missing:
 - If year = year of first dose, then set month and day to month and day of first dose.
 - If year < year of first dose, then set month and day to December 31.
 - If year > year of first dose, then set month and day to January 1.
- If month and year are present and day is missing:

- If year = year of first dose and
 - month = month of first dose, then set day to day of first dose date.
 - month < month of first dose, then set day to last day of month.
 - month > month of first dose, then set day to first day of month.
- If year < year of first dose, then set day to last day of month.
- If year > year of first dose, then set day to first day of month.
- For all other cases, set date to date of first dose.

Adverse event end date

- If year is present and month and day are missing, or year and day are present and month is missing, set end month and day to December 31.
- If month and year are present and day is missing, set the day to last day of the month.
- If fatal event, date is set to minimum of imputed end date and death date.
- For all other cases, set date to missing.

Concomitant medication

- If start date is completely missing, start date will not be imputed.
- If start year is present and month and day are missing, or year and day are present and month is missing, set start month and day to January 1.
- If start year and month are present and day is missing, set start day to 1st day of month.
- If end date is completely missing, end date will not be imputed.
- If end year is present and month and day are missing, or year and day are present and month is missing, set end month and day to December 31.
- If end year and month are present and day is missing, set end day to last day of the month.

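### The treatment-emergent rule and the AE onset imputation, as written, can flag some events that predate the first dose as treatment-emergent

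*SAP*

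**What the plan says.** **Collection window.** SAP 10.3: "The AE eCRF has been designed to capture all events from time of signing the informed consent through the Safety Follow-up visit". Protocol 8.8 says the same. Protocol section 8, Screening Visits: "The Screening period starts at the time the ICF is signed and will be up to 8 weeks in duration". That section also allows a further 2 to 4 weeks after discussion with the Medical Monitor.

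**Treatment-emergent rule.** SAP 10.3 opens with "Treatment-emergent AEs (TEAEs) are defined as AEs with an onset date on or after the start of IMP treatment". The next sentence restates this as "TEAEs are all adverse events which started after start of IMP treatment" and adds a second route: "if the event was continuous from baseline and was worsening, serious, IMP related, or resulted in death, discontinuation, interruption or reduction of IMP". Protocol 8.8.1 has the same second route ("if the event was continuous from baseline and was worsening, serious, IMP related", and so on).

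**Onset imputation.** In SAP 5.4 a completely missing AE onset becomes the first-dose date. So does an onset with the month missing whose year is the year of first dose. Where only the day is missing and the year matches, the rule is "month = month of first dose, then set day to day of first dose date". An earlier month becomes the last day of that month. An earlier year becomes the last day of the recorded month, or 31 December if the month is missing.

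**Consistency check.** SAP 5.4 has one sentence requiring imputed dates to be logical, including that no end date falls before its start date. It is the last bullet of the concomitant-medication list. Neither the AE onset list nor the AE end-date list has a counterpart.

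**The concern.** A treatment-emergent table is meant to show what started or got worse after dosing. Two rules let in events that did neither.

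- The second route tests whether an ongoing event *is* serious, not whether it *became* serious after first dose. A screening SAE, unchanged on Day 1, would enter the treatment-emergent SAE table.
- The imputation resolves doubt about onset in favour of treatment even where a recorded end date leaves no doubt that the event was over.

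At stake are the TEAE and treatment-emergent SAE counts in every arm, some dilution of relative contrasts between arms, and an AE listing with impossible durations.

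**Working it through.** The documents state no count or rate on this point, so there is no figure of the plan to reproduce. The check is on the logic of the rules and on how often the imputation rule would act.

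**1. The second route.** Its conditions are joined by *or*. Take an AE with onset 20 days before first dose, serious, ongoing on Day 1, with no change afterwards. It fails the onset test and meets the second route on *serious* alone, so it is a TEAE and a treatment-emergent SAE. Protocol 8.8.2.1 limits the pool: a condition that predates the AE reporting period is not an AE unless it worsens or its episodes become more frequent. The route therefore admits events that started after consent, or earlier conditions that worsened after consent but before dosing.

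**2. What the imputation does.** SAP 5.4 applied as written:

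| First dose | Recorded onset | Imputed onset | Position |
|---|---|---|---|
| 15 Jun 2021 | Jun 2021 | 15 Jun 2021 | first-dose date |
| 15 Jun 2021 | 2021 only | 15 Jun 2021 | first-dose date |
| 15 Jun 2021 | none | 15 Jun 2021 | first-dose date |
| 15 Jun 2021 | May 2021 | 31 May 2021 | pre-treatment |
| 15 Jun 2021 | Apr 2021 | 30 Apr 2021 | pre-treatment |
| 15 Jan 2021 | Dec 2020, or 2020 only | 31 Dec 2020 | pre-treatment |

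**3. How often true screening onsets move.** Assumption, not in the documents: first doses and screening onsets are spread evenly over the days of a non-leap year.

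*Day missing.* With first dose on calendar day d, the d − 1 preceding days share its month. The mean of d − 1 over the year is (7 × 465 + 4 × 435 + 378) / 365 = 5373 / 365 = 14.72 days.

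- 56-day screening: 14.72 / 56 = 26%, ranging from 0% (d = 1) to 30 / 56 = 54% (d = 31).
- 70 days: 14.72 / 70 = 21%.
- 84 days: 14.72 / 84 = 18%.
- Shorter screening raises the share: 52% for 28 days and 75% for 14 days, by enumerating every date.

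*Month missing, year known.* On day j of the year, min(j − 1, 56) of the 56 screening days fall in the same year. The average share is (1596 + 308 × 56) / (365 × 56) = 18844 / 20440 = 92%. For 84 days it is (3570 + 280 × 84) / (365 × 84) = 27090 / 30660 = 88%.

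*Fully missing.* 100%.

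These are shares of incompletely dated screening onsets, not of all AEs.

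**4. The end-date conflict.** Onset recorded as March 2021, end 5 March 2021, first dose 20 March 2021. The month and year match, so onset becomes 20 March, Study Day 1. By the study-day formula in SAP section 5 the resolution day is 5 − 20 = −15. The event is a TEAE under the first sentence of SAP 10.3 and resolves before it starts.

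**5. The two onset wordings.** An onset imputed to the first-dose date is treatment-emergent under *on or after* but not literally under *after*. The two sentences give different answers for exactly the events that step 2 moves.

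**6. Scale.** With about 100 subjects per arm, one wrongly flagged subject is at most 1 percentage point, and less if that subject has another qualifying event. As an illustration only, assume true rates of 30% and 20% and an independent proportion m wrongly flagged in each arm, so that the observed rate is p + (1 − p)m.

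- m = 1%: 30.7% and 20.8%; difference 9.9 points, ratio 1.48.
- m = 3%: 32.1% and 22.4%; difference 9.7 points, ratio 1.43.

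The true difference is 10 points and the true ratio 1.50.

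**The case against.** **The word *serious* could be read in context.** Its neighbours (IMP related, and discontinuation, interruption or reduction of IMP) can only arise after dosing, so *serious* may have been meant as becoming serious on treatment. That may be the intent, but the text does not say it, and a programmer following the list would flag on seriousness alone.

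**Few events are exposed.** Protocol 5.2.2 excludes subjects with several serious events during screening, such as acute coronary syndrome, stroke, heart failure hospitalization, deep vein thrombosis and pulmonary embolism, and with active bleeding or blood loss within 8 weeks before randomization. Protocol 8.8.2 asks for start and end dates and times, so partial dates should be uncommon. This stands, and it limits the size.

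**Assigning doubtful onsets to treatment is a deliberate conservative choice**, in line with SAP 10.3 imputing missing severity or causality to the worst category. This stands where timing is unknown, but not where a recorded end date settles it.

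**The check for logical dates may cover AEs.** Its wording is not limited to medication, and the example in step 4 would violate it. But it sits in the concomitant-medication list, and it does not say which date gives way. At best its reach to AE onset is unclear.

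**The consequences are visible.** The AE listing carries the TEAE flag and the onset and resolution days, all AEs and SAEs are summarized beside the treatment-emergent counts, and most safety analysis is descriptive. That helps a careful reader but does not correct the tables.

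A reader might infer that all partly dated screening events are moved to first dose, or that every serious condition present at baseline is counted. The documents do not support either. With a full 8-week screening, about three quarters of onsets lacking only the day stay pre-treatment under the assumption in step 3, and conditions predating consent are not AEs unless they worsen.

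**Conclusion.** The point holds in this limited form. As written, SAP 10.3 and protocol 8.8.1 count an AE that began between consent and first dose, and is ongoing at baseline, as treatment-emergent if it is merely serious. SAP 5.4 moves three defined kinds of incomplete onset to the first-dose date without checking a recorded end date. These are stated rules that give a wrong classification, not missing detail.

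The number of affected events cannot be computed. It depends on how many screening SAEs are unresolved at Day 1 and how many onset dates are incomplete, and the documents give neither. It is likely to be small. The rates in step 6 are assumptions that show scale only.

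A reader might also infer a bias toward one arm. None is expected from these two mechanisms: the affected onsets precede randomization and the rules are the same in every arm. The expected effect is modestly higher treatment-emergent counts throughout and slightly diluted relative contrasts. A chance imbalance of a few subjects is possible. It could matter for a preferred term near the 5% reporting threshold in SAP 10.3, since that is about 5 subjects in an arm of 100.

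**What to change.** - **SAP 10.3 and protocol 8.8.1.** For events ongoing at first dose, require that the qualifying change (worsened, became serious, judged IMP-related, or led to death or an IMP action) occurred after first dose. Use a single *on or after* wording for onset in both sentences.
- **SAP 5.4, AE onset.** If a known AE end date precedes first dose, impute onset no later than that end date and do not flag the event as treatment-emergent.

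The cost is two SAP sentences, the matching protocol wording and one programming check. No new data are needed, because the AE start date, end date, severity, seriousness, causality and action taken are already recorded. SAP section 1 gives the SAP precedence over the protocol for analysis, so the SAP change can govern the tables while protocol 8.8.1 is brought into line.
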